### Inclusion Criteria:

1. Metastatic breast cancer (Stage IV)
2. Histologically confirmed estrogen receptor positive disease
3. Female
4. Serum 25(OH) <30 ng/ml
5. Age  $\geq$  18 years
6. Pre or post-menopausal
7. ECOG Performance status 0-2
8. Adequate organ function as defined as GFR > 30 mls/min and serum calcium  $\leq$  10.4 mg/dl
9. Any race/ethnicity
10. English speaking
11. No changes to MBC treatments within 30 days of enrollment and/or deemed clinically stable by their treating physician
12. Willingness to sign a written informed consent and complete questionnaires
13. Cease ingestion of vitamin D supplementation not study related

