Other Factors	Demographics and cancer history	Age, race, employment, home life, treatments	Individual, Physiological	0
	Diet	Calcium/Vit D & Fruit, vegetable, fiber screeners	Biological	0
	Obesity	Body composition, Anthropometrics	Physiological	0,8
	Physical activity	Godin	Physiological	0,8
	Support	MOS Social Support	Environmental	0,8
	Sunlight	Sun exposure tool	Physiological	0,8

**vii. Laboratory Outcomes:** Laboratory analyses will be conducted by the Core Laboratory of LUHS, within a Basic Science Laboratory at LUHS and/or by Quest Diagnostics. Serum vitamin D and serum

estradiol will be measured using liquid chromatography/tandem mass spectrometry (LC-MS/MS). This technique is considered the 'gold standard,' providing total 25(OH)D which includes vitamin D2 and vitamin D3, as well as total serum estradiol levels. Calcium will be quantified by spectrophotometry. Biomarkers of inflammation (e.g., C-reactive protein (high sensitivity), interleukins, TNF- $\alpha$ ) will be measured at baseline and follow up with the laboratory analyses conducted in batch to decrease intra-assay variability. The comprehensive metabolic panel (CMP) will be completed to assess baseline organ function, and includes albumin, alkaline phosphatase, ALT, AST, calcium, CO2, BUN/Creatinine, chloride, creatinine with estimated GFR, globulin (calculated), glucose, urea nitrogen, potassium, sodium, total bilirubin, and total protein.

**viii. General well-being outcomes:** To increase comparability across studies, the selected tools have been used previously in breast cancer and/or other cancer populations. (Copies of the tools can be found in the Appendices.)

*Demographics and treatment:* Similar to our previous study, we will obtain information on age, race/ethnicity, employment status, living situation, diagnosis, treatments (medical, surgical and radiation) and metastatic sites.

*Brief Pain Inventory-Short Form:* This validated instrument was designed to assess pain in cancer patients. It includes four items measuring the severity of pain in the last 24 hours on a scale of 0–10, plus seven additional items measuring the extent to which pain interferes with life activities.

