## **VII. Safety Monitoring Plan**

- a.** Published reports suggest that 50,000 IUs of vitamin D taken *daily* can increase vitamin D levels to more than 150 ng/dl and cause hypercalcemia. The proposed dosing for this study is 50,000 IUs per week, which equates to ~7,000 IUs/day. This dose has minimal side-effects in healthy populations, but may include bone pain, constipation, dry mouth, headache, stomach upset and loss of appetite. We will be monitoring laboratory values at baseline and 8 weeks, and patient symptoms at baseline, 4 and 8 weeks.
- i. Any patient who receives treatment on this protocol will be evaluable for toxicity. This study will utilize the CTCAE (NCI Common Terminology Criteria for Adverse Events) Version 4.0 available at (<http://ctep.cancer.gov>). Participants will be called after 4 weeks of supplementation to ascertain pill counts, gauge their general tolerance and capture symptom management data related to pain, fatigue, mood, sleep and overall health. Although toxicity and adverse side-effects from vitamin D3 supplement are rare, participants will be queried their general tolerance to the study medication during the 4 week phone call. The following criteria will be utilized to determine supplement suspension or supplement discontinuation: .If the participant develops Grade 1 toxicity that is felt to be possibly, probably, or definitely related to study supplement, the participant will continue to be monitored.
  - ii. If the participant develops Grade 2 toxicity that is felt to be possibly, probably, or definitely related to study supplement, the participant may go on study supplement holiday until toxicities are Grade 1 or lower (for no longer than 4 consecutive weeks).
  - iii. If a participant develops any Grade 3 or Grade 4 or has persistent Grade 2 toxicity beyond four consecutive weeks possibly, probably, or definitely related to the study supplement, the study supplement will be discontinued. A blood draw at the nearest Quest Diagnostics facility or the Cardinal Bernadin Cancer Center Phlebotomy Laboratory will be procured to obtain 25(OH)D and a comprehensive metabolic profile.

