  - iv. If a participant's serum calcium and corrected calcium\* exceeds 10.5 mg/dL, then study supplement will be suspended. The participant will be encouraged to lower any calcium intake and provided a handout on calcium sources. The serum calcium will be rechecked in two weeks and the participant may continue on study supplement if the serum calcium is below 10.5 mg/dL. Otherwise, the participant will be removed from study intervention. The participant may also be removed from study intervention for any Grade 2 or higher hypercalcemia (serum calcium > 11.5 mg/dl).  
\*Corrected calcium = serum calcium + [(4.0 – serum albumin) x 0.8]
  - v. In each of these cases, the follow up questionnaires and follow-up blood analyses will still be collected as per protocol eight weeks after the initial start of the intervention.
- b.** Participants may be re-challenged following a suspension. Specifically, participants who have had a study physician-ordered dose suspension may be re-challenged by returning to the full dosage, or

the study physician may decide to have the participant continue her participation on a reduced dose (e.g., 25,000 IUs/week) until study completion.

- c. A participant will be taken off study if she experiences any of the following adverse events: 1) hypercalcemia (>11.5 mg/dL), 2) a serum 25(OH)D level >100 mg/dL with normal calcium or symptoms of vitamin D indicating possible toxicity, 3) clinically significant increases in serum estradiol indicating a potential drug-nutrient interaction, or 4) has intolerable side-effects believed to be associated with vitamin D3 supplementation. Serious and/or unanticipated adverse events will be reported to the Loyola IRB within 24 hours of occurrence.
- d. To ensure the safety of participants, we will complete an exhaustive review of all safety measurements employed in this study after 7, 19, and 25 patients are enrolled. This includes examining their laboratory values, adverse event logs, and notifications in order to make a determination about whether the study should continue for all participants or whether the study should terminate.

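### The calcium suspension rule does not say whether both values or either value must exceed 10.5 mg/dL, and its restart test omits the albumin-corrected value

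*Protocol*

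**What the plan says.** Protocol section VII.a.iv sets the calcium rule for Group 1.

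- **Suspension:** the supplement is suspended when "serum calcium and corrected calcium" exceeds 10.5 mg/dL. The verb is singular, and neither *both* nor *either* appears.
- **Correction:** the footnote gives "Corrected calcium = serum calcium + [(4.0 – serum albumin) x 0.8", closed by a bracket. Serum calcium is therefore the uncorrected input to the formula.
- **Recheck and restart:** serum calcium is repeated after two weeks, and the participant "may continue on study supplement if the serum calcium is below 10.5 mg/dL". If it is not, she is removed from the intervention. Corrected calcium and albumin are not mentioned at this step.

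Three other places bear on the rule.

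- **Entry:** inclusion criterion 8 reads "Adequate organ function as defined as GFR > 30 mls/min and serum calcium" at or below 10.4 mg/dL, again uncorrected.
- **Albumin:** section VI.a.vii says the comprehensive metabolic panel (CMP) "includes albumin, alkaline phosphatase, ALT, AST, calcium" and other analytes, and ties it to baseline organ function. Corrected calcium can therefore be computed before dosing.
- **Timing:** section VII.a says "We will be monitoring laboratory values at baseline and 8 weeks".

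The SAP does not deal with calcium monitoring.

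**The concern.** A correction for albumin is normally added so that a low albumin does not hide a raised calcium. Section VII.a.iv brings in such a correction, joins it to serum calcium with a bare *and*, and then drops it at restart. Two staff members could apply the sentence differently to the same result. Depending on the reading, the correction either does nothing where it would matter, or suspends a woman who already qualifies to resume.

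Hypercalcemia is one of the two safety concerns that the protocol names for this supplement (section III), and Aim 1 is repletion without adverse effects. At stake is whether a woman with low albumin and raised corrected calcium stays on, or returns to, 50,000 IU per week.

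**Working it through.** **Inputs.** The 10.5 mg/dL suspension and restart limits and the correction formula come from section VII.a.iv. The 10.4 mg/dL entry limit comes from inclusion criterion 8. All albumin values below are assumptions, as is the unit g/dL, which the protocol does not print. The plan gives no figure of its own to reproduce.

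Write S for serum calcium, A for albumin and C for corrected calcium:

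C = S + 0.8 × (4.0 − A)

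**Reading 1: both values must exceed 10.5.** The rule is min(S, C) > 10.5.

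- If A is 4.0 or lower, C is at least S. The smaller value is S, so the rule reduces to S > 10.5 and the correction has no effect.
- If A is above 4.0, C is below S. The rule becomes C > 10.5, that is S > 10.5 + 0.8 × (A − 4.0). At A = 4.2 this needs S above 10.66; at A = 4.5, above 10.90.

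So, compared with serum calcium alone, the correction can cancel a suspension but never add one. An enumeration over S from 8.00 to 13.00 in steps of 0.01 and A from 2.0 to 5.5 in steps of 0.1 agrees: 0 combinations added and 960 removed. These are counts of combinations, not of patients.

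**Reading 2: either value is enough.** The rule is max(S, C) > 10.5. Take S = 10.4 and A = 3.5. Then C = 10.4 + 0.8 × 0.5 = 10.80, which suspends. The restart test is S < 10.5, and 10.4 passes it. The value that stopped her would also let her resume.

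**Reading 3: corrected calcium governs.** The rule is C > 10.5. The same example shows the same conflict with a serum-only restart.

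**Readings side by side, with the proposed restart (both values below 10.5):**

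| S | A (assumed) | C | Suspend: both | Suspend: either | Suspend: corrected only | Restart now (S < 10.5) | Restart proposed |
|---|---|---|---|---|---|---|---|
| 10.4 | 4.0 | 10.40 | no | no | no | yes | yes |
| 10.4 | 3.5 | 10.80 | no | yes | yes | yes | no |
| 10.0 | 3.0 | 10.80 | no | yes | yes | yes | no |
| 10.6 | 4.0 | 10.60 | yes | yes | yes | no | no |
| 10.6 | 4.2 | 10.44 | no | yes | no | no | no |

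**Strictness of the fix.** Any result that suspends under *both*, under serum alone or under corrected alone also suspends under *either*. Any result with both values below 10.5 also has serum calcium below 10.5. The proposed pair is therefore never looser than the current text.

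**Entry.** C passes 10.5 when A falls below 4.0 − (10.5 − S)/0.8. That is 3.875 at S = 10.4, 3.625 at S = 10.2 and 3.375 at S = 10.0. Criterion 8 admits all three serum values.

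**The case against.** The strongest reply is that this is loose drafting, not a bad rule. The singular verb does not suit a deliberate two-part condition, and it is hard to see why anyone would add a formula only to make suspension harder. On that view the authors meant *either*, or meant calcium as corrected, and the finding about an inert correction falls away. That is fair about intent. A reader might infer that the protocol definitely disables its own correction; the documents do not support that, because it holds only if both values are required. But the reply does not save the rule, since the other readings put trigger and restart in conflict.

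A second reply concerns the remedy. It is tempting to use corrected calcium alone throughout. That would be weaker than an *either* trigger. It would also let a woman at serum 10.6 and albumin 4.2 (corrected 10.44) resume at recheck, where the present text removes her. This objection stands, and the fix below avoids it.

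A third reply is that criterion 8 is clear as written and nothing in the documents requires a corrected value at entry. This also stands. A reader might infer that the entry rule contradicts the suspension rule; it is a clinical choice, and changing it could cost enrolment in a pilot aiming for 25 women.

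A fourth reply is that the rule rarely acts. The only scheduled tests are at baseline and week 8, and the week 8 visit follows the course, so a.iv works during dosing mainly after an unscheduled draw. Restart is permissive, and the study physician decides on re-challenge (VII.b). Hypercalcemia above 11.5 mg/dL takes a participant off study (VII.c), and safety data are reviewed after 7, 19 and 25 patients (VII.d). Women with kidney stones, renal failure or hyperparathyroidism in their history are excluded, and the investigator may exclude on safety grounds. All of this limits the size of the point but does not give the sentence one meaning.

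**Conclusion.** The point holds as a defect of wording and consistency within section VII.a.iv. The trigger does not say whether both values or either value is meant, and the restart test leaves out the corrected value. Under *both*, the correction never adds a suspension. Under *either*, or if corrected calcium governs, a woman can be suspended and eligible to restart on the same result. This rests on the printed formula and limits alone; albumin assumptions enter only the worked examples.

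The practical effect is small, for the reasons of timing and safeguards given above, and no endpoint or analysis changes. A reader might infer that a known share of women would be dosed while hypercalcemic. The documents do not support any count, because they give no calcium or albumin distribution. To show how little assumptions settle, take normal distributions with serum calcium mean 9.2 to 9.6 (SD 0.4 to 0.6), albumin mean 3.6 to 4.0 (SD 0.3 to 0.5) and correlation 0.3 to 0.5. The expected number of 25 eligible women with corrected calcium above 10.5 then runs from 0.0 to 2.9, too wide to use as an estimate. The point merits a clarifying amendment and nothing heavier.

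**What to change.** Amend VII.a.iv in two places.

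1. **Suspension:** suspend if serum calcium *or* corrected calcium is above 10.5 mg/dL.
2. **Recheck:** after two weeks draw calcium and albumin in the same sample, and allow restart only if *both* serum and corrected calcium are below 10.5 mg/dL. Otherwise remove the participant from the intervention, as now.

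The cost is one albumin per recheck, and possibly a few more suspensions and removals among women with low albumin. Follow-up data would not be lost by design, because VII.a.v already keeps the eight-week questionnaires and blood tests after a suspension or removal.

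Optional, and not the correction of an error: also check corrected calcium at entry. Criterion 8 would admit a woman at serum 10.4 and albumin 3.5, whose corrected calcium of 10.80 is already above the suspension limit. Albumin is in the baseline CMP, so no new test is needed. The cost is the loss of some women who are eligible now, in a number that the documents do not allow one to state.

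### Calcium above 11.5 mg/dL falls under two conflicting stopping rules: one keeps week-8 follow-up, the other removes the woman from the study and states none

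*Protocol*

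**What the plan says.** Section VII of the protocol places its stopping rules in two separate items.

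**Item a.** Under a.iii, related Grade 3 or 4 toxicity, or related Grade 2 toxicity lasting beyond four weeks, means that "the study supplement will be discontinued". A blood draw then "will be procured to obtain 25(OH)D and a comprehensive metabolic profile"; section VI.a.vii confirms that this panel "includes albumin, alkaline phosphatase, ALT, AST, calcium". Under a.iv, calcium above 10.5 mg/dL suspends the supplement. "The serum calcium will be rechecked in two weeks", and she may resume if the value is below 10.5. For values above 11.5 the same item adds: "The participant may also be removed from study intervention for any Grade 2 or higher hypercalcemia". Item a.v closes the list: "In each of these cases, the follow up questionnaires and follow-up blood analyses will still be collected as per protocol", eight weeks after the start of the intervention.

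**Item b** permits re-challenge, at full or reduced dose, after a suspension ordered by the study physician.

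**Item c** opens with "A participant will be taken off study if she experiences any of the following adverse events". It lists four events: calcium above 11.5 mg/dL (c.1), 25(OH)D above 100 (c.2), a clinically significant estradiol rise (c.3), and that she "has intolerable side-effects believed to be associated with" the supplement (c.4). Item c does not define what being off study means and says nothing about follow-up.

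Table 1 schedules 25(OH)D, calcium, estradiol, FACT-B, FACT-ES and handgrip at weeks 0 and 8 only. Pain, fatigue, mood, sleep and overall health are also assessed at week 4.

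**The concern.** The two rules for calcium above 11.5 mg/dL differ in verb (*may* against *will*) and in object (the intervention against the study). The text does not say which one governs. Two things follow.

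The first is patient management. Under a.iv and item b a woman could be rechecked and put back on the supplement. Under c.1 she could not.

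The second is the data. If leaving the study ends data collection, a woman removed before week 8 has no week-8 25(OH)D, calcium or estradiol and no post-baseline FACT-B, FACT-ES or handgrip. She then contributes no pair to the paired t tests (protocol, section VIII) or the signed rank tests (SAP). Hypothesis 1 says that calcium and estradiol will not change significantly, and c.1 and c.3 remove women because of those same two variables. Any loss by this route would depend on the outcome.

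**Working it through.** **Step 1. The two rules side by side, calcium above 11.5 mg/dL**

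| | Items a.iv and a.v | Item c.1 |
|---|---|---|
| Removal | optional | mandatory |
| Removed from | study intervention | study |
| Resumption | possible after a recheck below 10.5 | none stated |
| Week-8 data | still collected | not stated |

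**Step 2. One woman under both rules.** Suppose an early unscheduled draw shows 11.8 mg/dL, and her corrected calcium is also above 10.5. Under a.iv she is suspended and rechecked in two weeks. If she is then below 10.5 and the physician has not chosen to remove her, she may resume, and week-8 collection stands. Under c.1 she leaves the study. Both courses follow the written protocol.

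**Step 3. When could week-8 data actually be lost?**

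- *High calcium first seen at week 8.* Nothing scheduled is lost, because section VI.a.ix puts the final bloods and questionnaires at that visit.
- *High calcium at baseline.* She is not eligible, because entry requires calcium of 10.4 mg/dL or less.
- *Estradiol (c.3).* It is scheduled at weeks 0 and 8 and is not in the a.iii draw, so no draw ordered by the protocol would show a rise earlier.
- *The a.iii stopping draw.* It can show high calcium or 25(OH)D before week 8. The woman is already an a.iii case, though, and a.v keeps her week-8 collection. Loss requires item c to override a.v.
- *The a.iv recheck.* It falls before week 8 only if the first high value was found early.
- *Intolerable side-effects (c.4).* No laboratory value is needed, so this can occur in any week. It may overlap with toxicity handled under item a, but the text does not equate the two.
- *A result from routine care.* This is possible, but the protocol does not describe it.

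The main remaining routes are early c.4 events and unscheduled early results.

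**Step 4. Size per woman.** Section V.c gives 25 women recruited and about 20% attrition: 25 × (1 − 0.20) = 20 with complete data, which reproduces the plan's figure. So the plan already accepts 25 − 20 = 5 women without complete data.

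Let N women be due a week-8 value and let one be omitted. Of the other N − 1, x are sufficient; y is 1 if the omitted woman is sufficient and 0 if not.

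Shift in the proportion = x/(N − 1) − (x + y)/N

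- y = 0: shift = x/[N(N − 1)], largest at x = N − 1, giving +1/N.
- y = 1: shift = −(N − 1 − x)/[N(N − 1)], largest in size at x = 0, giving −1/N.

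The shift is therefore at most 1/N in size: 1/25 = 4 percentage points, or 1/20 = 5 points.

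For a mean change, let d be her change minus the mean of the others. Omitting her shifts the mean by −d/N, which is 4% or 5% of d. The documents do not give d. With an assumed d of +2.0 mg/dL for calcium and N = 20, the mean change reads 2.0/20 = 0.1 mg/dL too low.

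**Step 5. Number of women.** The documents give no rate of calcium above 11.5 mg/dL. At assumed rates of 1%, 2%, 5% and 10%, the expected number among 25 is 0.25, 0.5, 1.25 and 2.5. These count any such value. Only those found before week 8 could lead to loss, so the number lost through c.1 would be smaller.

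**The case against.** The strongest reply is that this is a loose phrase with almost no consequence. Being off study may simply mean off the supplement, in which case a.v can be read to apply. The visit schedule nearly closes the calcium route, and the one early draw that the protocol orders arises in a case that a.v covers. All treated women remain evaluable for toxicity (a.i), and the item d reviews still see laboratory values and event logs. This is a 25-woman pilot with no formal sample-size calculation.

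Most of that stands, and it limits the consequence. It does not remove the conflict. The text neither gives the lenient reading nor links item c to a.v, and the difference in management at 11.5 mg/dL exists whether or not any data are lost.

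Two stronger readings are tempting, and the documents do not support either:

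- *Mild harm is followed and severe harm is lost.* Item a.v also covers a.iii, which includes related Grade 3 and 4 toxicity, so the protocol states follow-up for severe cases too.
- *The drop-out text in section VI.a.x shows that follow-up ends.* That text concerns women who drop out. It does not clearly govern removal by the investigators, and it does not say that week-8 collection stops.

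**Conclusion.** The conflict is definite: at the same calcium threshold the protocol gives an optional and a mandatory rule, with different objects, and states follow-up for only one. The loss of week-8 data is conditional. It requires a literal reading of item c and an event before week 8.

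Few women are likely to be affected, but neither their number nor the size of any bias can be derived from the documents. Each omission moves the repletion percentage by at most 4 to 5 points, and a mean change by 4% to 5% of that woman's distance from the others. This is small beside the five incomplete cases that the plan already allows. What deserves correction is that such a loss would depend on harm, and that stopping and re-challenge are inconsistent. A reader might infer that the calcium conflict is a material source of missing data in this trial; the visit schedule does not support that. The point should be fixed, but on its own it does not undermine the study.

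**What to change.** **Wording, before the text is reused in the planned larger trial.** In item c, replace *taken off study* with *permanently taken off study supplement*, and add: *Item a.v applies to c.1 to c.4 unless she withdraws consent.* Use the same verb in a.iv and c.1 for calcium above 11.5 mg/dL. The choice belongs to the study physicians; *will* is the safer reading and rules out re-challenge at that level.

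**Reporting, for this study.** The SAP is dated November 2018 and describes analyses already done. It places its change analysis among women treated for 8 weeks and does not say whether early stoppers with week-8 data are included. The report should therefore give the number removed under each of c.1 to c.4, the week of removal, whether week-8 data were collected, and whether those women are in the signed rank tests.

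**Cost.** A short text change, and a count from existing logs. Under the new wording a few women would attend week 8 after stopping, and their values would include time off supplement. Item a.v already accepts both for other women who stop.

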### III. Study Aims

Several clinical trials are underway to investigate if vitamin D2 or D3 provided at various doses (10,000-50,000 IUs/week) can improve the side-effects associated with anti-estrogen therapies, specifically aromatase inhibitors (AIs). However, these current trials use variable forms of vitamin D and predominantly include women with Stage I-III disease, excluding women with metastatic breast cancer. Evaluation of the safety of vitamin D3 supplementation is crucial since supplementation can lead to hypercalcemia and importantly, *in vitro* studies have shown that vitamin D3 influences the transcription of a gene that increases estrogen production. To assure that vitamin D3 does not abrogate the clinical effects of anti-estrogen therapies, the effect of vitamin D3 supplementation on estrogen production requires evaluation. Therefore, the overarching goal of this pilot study is to evaluate the safety, feasibility and efficacy of vitamin D3 supplementation in women with MBC. We will address and test the following aims and hypotheses, respectively:

**Aim 1:** To determine if weekly supplementation of 50,000 IUs of vitamin D3 raises serum levels of 25(OH)D to >30 mg/dl without adverse effects.

**Hypothesis 1:** Women who are compliant with vitamin D3 supplementation, as evidenced by normalization (>30 mg/dl) or increases in their serum 25(OH)D levels, will not experience significant changes in serum calcium or serum estradiol levels.

**Aim 2:** To determine the effect of vitamin D3 supplementation on symptom management.

**Hypothesis 2:** Women who achieve serum concentrations of 25 (OH)D ≥30 mg/dl or experience significant increases in 25(OH)D will exhibit improvements in pain, fatigue, sleep, mood, muscle function and overall quality of life.

**Exploratory Aim:** To explore the mechanistic effects of serum vitamin D levels and vitamin D3 supplementation on inflammatory markers and potential associations with symptom management.

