**d. Study endpoints:** The primary endpoint in this study is serum 25(OH)D. We will use this serum biomarker to assess if repletion levels are obtained ( $\geq 30$  ng/dl), to test associations with symptoms and/or to assess the degree of change from baseline to follow up. Serum calcium and serum estradiol levels will be monitored to be sure these levels normalize or to assess clinically significant changes following supplementation, respectively.

To address our secondary endpoints, we will be assessing symptoms, including pain (Brief Pain Inventory; Cleeland, 1994; FACT-Bone pain, Broom, 2009), fatigue (Piper Fatigue Scale; Piper, 1998), mood (Hospital Anxiety and Depression Scale; Herrmann, 1997; Patient Health Questionnaire-8; Kroenke, 2001), muscle function (handgrip strength), sleep (Pittsburg Quality Sleep Index; Carpenter, 1998), overall health and QOL (FACT-B; Brady, 1997; FACT-ES; Fallowfield, 1999.) These specific tools were selected because they have been utilized in breast cancer populations and/or other cancer populations and will provide the ability to compare our findings to others. In addition, to address important confounders, we will gather data on diet (Block Calcium/Vitamin D screener; Cummings, 1987), physical activity (Godin Leisure Time Activity, 1985), body composition (bioelectrical impedance, dual energy x-ray

absorptiometry), sunlight exposure (Glanz sunlight exposure, 2008), social support (Multiple Outcomes Social Support; Sherbourne, 1991) and previous/current breast cancer treatments.

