## **VI. Study Procedures**

**a. Study subject procedures:** Subjects must meet all of the inclusion and none of the exclusion criteria to be enrolled into the intervention arm of the study. In addition, women meeting all of the inclusion and exclusion criteria except the serum 25(OH) cut point will be offered the opportunity to participate in the cross-sectional arm of the study.

i. The following criteria will be used to assess eligibility and participation.

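### Serum 25(OH)D thresholds are given in three incompatible units, so the repletion cut-off and the off-study limit do not work as written

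*Protocol*

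**What the plan says.** Twelve numeric 25(OH)D levels appear in the current protocol text, in three units.

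- **ng/ml (2):** inclusion criterion 4, "Serum 25(OH) <30 ng/ml", and its mirror, exclusion criterion 2 (≥30 ng/ml).
- **mg/dl (8):** the abstract's Methods (twice); II.e; Aim 1, which asks whether the dose "raises serum levels of 25(OH)D to >30 mg/dl without adverse effects"; Hypothesis 1, which refers to "normalization (>30 mg/dl) or increases in their serum 25(OH)D levels"; Hypothesis 2 (≥30 mg/dl); VI.a.iv; and VII.c.
- **ng/dl (2):** V.d, where the repletion level is ≥30 "ng/dl), to test associations with symptoms and/or to assess the degree of change from baseline to follow up"; and VII.a, which cites 150 ng/dl as a level seen with daily 50,000 IU dosing.

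The off-study rule in VII.c lists, as its second trigger, "a serum 25(OH)D level >100 mg/dL with normal calcium or symptoms of vitamin D indicating possible toxicity".

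Entry is tied to the formal lists: "Subjects must meet all of the inclusion and none of the exclusion criteria to be enrolled into the intervention arm of the study". Group 2 consists of "women meeting all of the inclusion and exclusion criteria except the serum 25(OH) cut point".

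Protocol section VIII plans a count of women who reach sufficiency after treatment and a logistic regression comparing them with those who do not. It gives no number or unit. The SAP splits women by sufficiency at baseline, also without a number or unit. It lists neither a week-8 repletion count nor the regression.

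**The concern.** V.d names serum 25(OH)D as the primary endpoint, and Aim 1 is framed around passing 30. A reader who wants the cut-off for that result finds one value in the aim, another in the endpoint section and a third in the eligibility list. VII.c is a rule for removing individual participants in a study with a stated safety purpose, and its numeric limit is in the wrong unit. It sits next to calcium limits that are properly in mg/dL, so nothing on the page signals the error.

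At stake are the dichotomous Aim 1 result, the regression built on it and one removal trigger. The protocol also says the findings will be used to design a larger trial, so the wrong figures could be carried forward.

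**Working it through.** The thresholds are stated, not calculated, so there is no derivation to reproduce. The check is whether they agree with each other and with the entry criterion.

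**Conversions.** 1 mg/dl = 1,000,000 ng per 100 ml = 10,000 ng/ml. 1 ng/dl = 0.01 ng/ml.

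| Place | As written | In ng/ml | Ratio to 30 ng/ml |
|---|---|---|---|
| Inclusion 4, exclusion 2 | 30 ng/ml | 30 | 1 |
| Aim 1, Hypotheses 1 and 2, II.e, abstract, VI.a.iv | 30 mg/dl | 300,000 | 10,000 |
| V.d | 30 ng/dl | 0.3 | 1/100 |
| VII.c | 100 mg/dL | 1,000,000 | 33,333 |
| VII.a (background) | 150 ng/dl | 1.5 | 1/20 |

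**Repletion.** The two versions differ by 300,000 / 0.3 = 1,000,000. Under the Aim 1 unit no woman could be classed as replete. Under the V.d unit, any woman entering at 0.3 to <30 ng/ml is already replete at baseline. That is (30 − 0.3)/30 = 99% of the entry interval (a share of the numeric range, not of patients).

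**Can the mg/dl figures be reached?** This step needs two assumptions that the documents do not give: 40 IU = 1 microgram, and a plasma volume of 1 to 5 L.

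- Full course (VI.a.v): 8 × 50,000 = 400,000 IU; 400,000 / 40 = 10,000 micrograms = 10 mg.
- If all of it stayed in plasma as 25(OH)D: 10 mg / 10 dl = 1.0 mg/dl at 1 L; 10 mg / 50 dl = 0.2 mg/dl at 5 L. The starting level (<30 ng/ml = <0.003 mg/dl) is negligible.
- 100 mg/dL is therefore 100/1.0 = 100 to 100/0.2 = 500 times what the whole course could produce. 30 mg/dl is 30/1.0 = 30 to 30/0.2 = 150 times.
- Even with a tenfold error in the IU conversion at 1 L (giving 10 mg/dl), the two limits remain 10 and 3 times too high.

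**How much of VII.c fails?** The wording allows two readings. If the symptoms clause stands alone, only the limb for a high level with normal calcium is lost. If it qualifies the level, the whole second trigger is lost.

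**What does not depend on the unit?**

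- The limb of Hypothesis 1 that rests on a rise, and that of Hypothesis 2 ("or experience significant increases in 25(OH)D will exhibit improvements in pain").
- The change and association uses in V.d.
- The paired tests in protocol section VIII and the signed-rank tests in the SAP.
- Entry to Group 1, and the SAP's baseline split, which follows from the ng/ml lists.

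**Operators.** Aim 1 and Hypothesis 1 use >30; II.e, Hypothesis 2, V.d and exclusion criterion 2 use ≥30. This matters only for a value of exactly 30.

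**The case against.** The strongest reply is that nobody would apply the literal units. The numeral is 30 everywhere, the eligibility lists give ng/ml, and section VIII speaks of sufficiency in the same terms as the SAP, so the week-8 count can be recovered by the same route as the baseline split. The SAP describes completed analyses and lists nothing that uses the repletion cut-off. The very large ratios measure the gap between unit prefixes, not an effect on the trial.

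The safety argument is also thin. Scheduled 25(OH)D is drawn only at weeks 0 and 8, and the week-8 draw follows supplementation. The one other specified draw (VII.a.iii) comes when the supplement is already being stopped for toxicity. The calcium rules (10.5 and 11.5 mg/dL), the toxicity-grade, estradiol and side-effect rules, and the reviews after 7, 19 and 25 patients all work regardless.

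Most of this stands, and it limits the consequence. It does not remove the error. The ng/ml lists govern who enters; they state neither the repletion rule nor the removal limit. Reading 30 ng/ml into Aim 1 is a safe inference. Reading 100 ng/ml into VII.c is plausible, because 100/30 = 3.3 gives a sensible scale, but the documents do not say so.

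**Conclusion.** The concern holds. The repletion cut-offs in Aim 1 and V.d contradict each other by a factor of 1,000,000, and both contradict the entry criterion. The numeric limit in VII.c, about 33,333 times the entry cut-off, cannot be reached. Those ratios need only metric conversion; the mass balance rests on the stated assumptions and serves as a plausibility check.

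The likely origin is drafting, and there is no sign that any result or patient decision used the literal units. The analytic effect is confined to the dichotomous repletion result and the exploratory regression in protocol section VIII. The safety effect is small, since even a corrected limit would rarely stop a dose. It should be corrected because a threshold for the primary endpoint and a participant-level removal limit are wrong on the page.

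**What to change.** - State every 25(OH)D level in ng/ml.
- Define sufficiency as ≥30 ng/ml in the abstract, II.e, Aim 1, Hypotheses 1 and 2, V.d and VI.a.iv. This changes > to ≥ in Aim 1 and Hypothesis 1, matching the other statements.
- Restate the VII.c limit as >100 ng/ml after the study physician confirms that this was intended, and say whether symptoms are a separate trigger.
- Check the unit of the 150 ng/dl figure in VII.a against its source.
- Add one line to the SAP or report giving the unit and cut-off actually used.

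The cost is protocol wording and one line in the SAP or report. No patients and no procedures are added.
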